Presentation of cocaine-paired cues elicits a stress response in cocaine-dependent individuals. Neuroimaging studies indicate substantial overlap in the corticostriatal limbic circuitry responsible for cue and stress-primed drug craving. Oxytocin receptors have been localized to these same regions and preclinical studies have shown that oxytocin attenuates the acute reinforcing properties of psychostimulants. Despite these findings, little is known about the role of oxytocin in modulating the affective response to cocaine-paired cues and associated neural activity in cocaine-dependent men and women and whether there are gender differences in this modulation.

**Hypothesis 2a:** Intranasal administration of oxytocin will decrease subjective ratings of cue-induced cocaine craving in cocaine-dependent men and women compared to placebo administration.

**Hypothesis 2b:** Intranasal administration of oxytocin will decrease functional activity in the anterior cingulate cortex, amygdala, striatum, and prefrontal cortex compared to placebo administration.

**Exploratory Hypothesis 2c:** The attenuation of functional activity in the anterior cingulate cortex, amygdala, striatum and prefrontal cortex following oxytocin administration will be greater in cocaine-dependent women as compared to cocaine-dependent men.

**Exploratory Hypothesis 2d:** Oxytocin will modulate resting-state and task-related functional connectivity among sub-networks implicated in reward and motivation (nucleus accumbens, and orbitofrontal cortex),

memory and learning (amygdala and hippocampus), and cognitive control (prefrontal cortex and anterior cingulate cortex). Oxytocin may increase connectivity between reward/motivation and cognitive control sub-networks in craving states as an index of top-down regulation.

**In summary**, the proposed project will provide important data on the effect of oxytocin on stress and craving in cocaine-dependent individuals, explore the neural circuitry involved in response to oxytocin administration, and investigate whether sex/gender differences in response exist.

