[figure not shown]

**Figure 3.** Results of the modularity partition based on the average correlation matrix among 90 regions in the rest (left) and cocaine (right) conditions of a cue-induced craving fMRI study of 37 cocaine users. Numbers indicate the region as specified in the AAL atlas and size of each node represents its average strength (i.e. sum of positive connections). Modules in the resting state include fronto-parietal (green), ventral-visual/temporal/orbitofrontal (red), dorsal visual (yellow) and basal ganglia/thalamus/auditory/insula (blue) sub-networks. Regions that reorganized when viewing cocaine images are noted by labels in the cocaine condition.

some of the same regions that have oxytocin receptors (e.g., amygdala, anterior/posterior cingulate, and striatum). Finally, [name], a major developer of the BCT, has agreed to be consultant on this project (see Letter of Support). He is currently integrating network-based statistics (Zalesky et al., 2010) into the BCT to allow for group comparisons of functional networks.

**C.1.e. Summary.** As demonstrated by the work above, the research team has experience with stress-induction studies ([name], [name], [name]), cue-reactivity research ([name], [name]), administration of oxytocin ([name]), neuroimaging ([name], [name], [name]), functional connectivity analyses ([name], [name]), and recruitment and retention of cocaine-dependent individuals for participation in laboratory-based studies ([name], [name]). Hence, the study team has the necessary skills to ensure the successful completion of the proposed study.

**C.2. Research Design and Methods.** In this project, the impact of acute pre-treatment with oxytocin (40 IU) or placebo on the subjective and physiologic response to the Trier Social Stress Task (TSST) in men and women with cocaine-dependence will be investigated. Additionally, participants will complete two functional magnetic resonance imaging (fMRI) scans in the presence of cocaine-related cues. Prior to each scan, participants will receive either oxytocin (OXY) or placebo (PBO) in a counter-balanced, double-blind fashion. A schematic of study procedures is shown below.

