
4. **Discharge.** Following the 60-minute assessment, participants will be given instruction regarding scanning appointments on days 2 and 3. A member of the research staff will be available to discuss management of any craving urges if craving remains elevated at the end of study procedures.

**c. fMRI Sessions.** On Days 2 and 3, participants will be asked to arrive at the ASD. Upon arrival, the participant will be breathalyzed and will provide a urine sample, which will be tested for substances and pregnancy (if applicable). If the pregnancy and urine drug tests are negative, with the possible exception of THC, the session will proceed. In the event that a participant tests positive, the scanning session will be rescheduled. Baseline subjective measures, physiologic measures (blood pressure and heart rate), and

salivary progesterone, estradiol, and cortisol will be collected. Individuals will then be escorted to the Center for Advanced Imaging Research (CAIR; see letter of support) by approved study personnel where MRI scans will be performed.

1. Medication Administration. At the beginning of the session, participants will be screened for metal using a handheld metal detector, and oxytocin (40IU) or placebo will be intranasally administered 40 minutes prior to cue exposure procedures. Although the pharmacokinetics of intranasal oxytocin are not fully understood (MacDonald et al., 2011), given the relatively short half-life of systemically administered oxytocin (approximately six minutes), we would not anticipate carry-over effects from repeated once daily dosing. Further, the order of administration will counterbalanced to obviate order effect; half of the participants will receive oxytocin prior to the first fMRI session and half will receive placebo.

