(SPM 8, The Wellcome Department of Cognitive Neurology, London). All volumes within a task run will be realigned to the first volume. After realignment (including adjustment for sampling errors), scans with greater than one mm in three axes or one degree in three orientations will be excluded from group analyses. Following realignment, images will be stereotactically normalized into a standard space with a resolution of 2x2x2 mm voxels using the Montreal Neurological Institute (MNI) EPI template in SPM8. Subsequently, the data will be smoothed with a 8x8x8 mm Gaussian kernel and will be high-pass filtered (cue exposure paradigm cut-off period = 288s). Following preprocessing, within-task data from individual participants will be analyzed with a fixed-effects general linear model (GLM), with cocaine cue exposure activity modeled as a box-car function convolved with the standard canonical hemodynamic response function. The GLM procedure is repeated for each voxel with six movement parameters (3 rotation values in radian and 3 translation values in millimeter) included as covariates to control for the influence of head motion on the data. First-level analysis will be conducted and contrast maps will be generated. For the cue exposure paradigm, the main contrast of interest is the cocaine pictures vs. neutral objects contrast. Following first-level analysis, subject-specific contrasts will be entered into second-level, random-effects analyses. Areas of brain associated with group (oxytocin vs. placebo) and sex (women vs. men) differences on these contrasts will be identified using independent samples t-tests within a GLM framework. The combined group parameter maps will be threshold using a significance level of  $p < 0.05$ , corrected for multiple comparisons.

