For Exploratory Hypothesis 2d, a graph-theory approach to functional connectivity will be used. The BCT (Rubinov & [name], 2011) includes metrics specifically designed for functional brain networks, which are fully connected with weighted and signed connections. The metrics combine both positive and negative weights, but weight the positive connections more heavily. Within each of 116 anatomical regions of the AAL atlas, the average intensity value at each time point will be extracted for each subject. The time series (shifted by one TR) will be segmented into four separate time series, one for each condition (cocaine images, blur, objects, rest) (Fair et al., 2007; Just et al., 2004). Correlation matrices will then be computed for each subject and each condition and submitted to the BCT. For each subject and each condition, several BCT metrics will be computed (see Rubinov & [name], 2011 for more details). Network measures include *modularity* and *number of modules*. Node-specific measures include *diversity coefficient*, *within-module weights*, *within-module clustering coefficient*, and *strength*. We will also compute 20 random networks for each subject that preserve the weight and strength properties of the cocaine network (following Rubinov & [name], 2011), since that is the network of most interest. The same metrics that are computed for the cocaine, object, blur, and rest networks will be computed for the 20 random networks, then averaged to provide a single metric for the random network. In addition, a group-average correlation matrix will be computed (Pearson r-values from individual participants are Fisher z-transformed prior to averaging) for each of the four conditions and subject groups to obtain a modularity partition for the group, which will be visualized using Gephi software (Bastian, Heymann, & Jacomy, 2009), as in Figure 4. Network and node-based metrics will be submitted to mixed ANOVAs (one ANOVA for each metric and each node in the case of node-based metrics) with gender and treatment as between-subjects variables and condition (cocaine, object, blur, rest, random) as the repeated factor. Most metrics allow for comparison with the random networks except for strength and weight metrics because those are preserved in random networks and will be identical to the cocaine condition.

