number of participants required is therefore estimated to be  $n=118$  ( $=140 \times 3.35/4$ ), which will be rounded to 120 to provide balance with respect to gender. Given an expected retention rate of approximately 80%, we will recruit 152 participants to obtain a final sample size of 120. This sample size will provide adequate power (80%) to detect the planned stress response, and more than adequate (98%) to detect the planned craving response to the TSST. In addition, the sample size of 120 participants will also provide 80% power to detect a 1 standard deviation differential in treatment effect between cocaine-dependent men and women for the craving response to the TSST. *Aim 2.* Existing fMRI studies involving cocaine cue exposure have included between 6 (Maas et al., 1998) and 17 (Garavan et al., 2000) participants per group, and have reliably found activation in brain regions associated with cocaine craving (e.g., anterior cingulate, amygdala). However, Mumford & Nichols (2008) simulation study suggested that 23 participants per group may be necessary to obtain 80% power for a generic fMRI task design featuring 10, 15-second task block and 10, 15-second rest blocks. As such, our proposed 60 completers participants per group should provide adequate statistical power.

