#### 1) General Inclusion / Exclusion Criteria

##### Inclusion Criteria

1. Subjects must be able to provide informed consent and function at an intellectual level sufficient to allow accurate completion of all assessment instruments.
2. Subjects must meet DSM-IV criteria for current cocaine dependence (within the past three months). While individuals may also meet criteria for abuse of other substances, they must not meet criteria for dependence on any other substance (except nicotine) within the last 60 days. Alcohol has been known to affect HPA function (Adinoff et al., 1991), however to enhance recruitment efforts individuals with alcohol dependence or abuse will be included in the study if they do not require medically supervised detoxification. Also, due to the high comorbidity of cocaine and marijuana dependence, and limited evidence that marijuana use affects HPA function, subjects with marijuana dependence will be included.
3. Subjects must consent to remain abstinent from all drugs of abuse (except nicotine) for a three-day period immediately prior to the throughout study procedures.
4. Subjects must consent to random assignment.
5. Subjects must consent to participating in study procedures at the ASD and completion of two fMRI scans.

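### Aim 2 scans each participant after both oxytocin and placebo, yet tests the drug effect as if the two sets of scans came from different people, and no sex-by-drug test is named for regional activity

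*Combined protocol and SAP*

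**What the plan says.** **Design.** Section C.2 (Research Design and Methods) has every participant complete two fMRI scans: "Prior to each scan, participants will receive either oxytocin (OXY) or placebo (PBO) in a counter-balanced, double-blind fashion". Section C.2.c.2, fMRI Sessions, Medication Administration, dismisses carry-over between the daily doses and balances the order: "half of the participants will receive oxytocin prior to the first fMRI session and half will receive placebo". Two scans are a condition of entry (Inclusion Criteria, item 5): "Subjects must consent to participating in study procedures at the ASD and completion of two fMRI scans". Each participant therefore receives both treatments.

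**Hypotheses.** Hypothesis 2b, which is not labelled exploratory, is a drug effect: "Intranasal administration of oxytocin will decrease functional activity in the anterior cingulate cortex, amygdala, striatum, and prefrontal cortex compared to placebo administration". Exploratory Hypothesis 2c asks whether that reduction is greater in women. Exploratory Hypothesis 2d concerns connectivity.

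**Analysis.** For regional activity, section C.2.d states that "group (oxytocin vs. placebo) and sex (women vs. men) differences on these contrasts will be identified using independent samples t-tests". For connectivity, the same section specifies mixed ANOVAs "with gender and treatment as between-subjects variables and condition (cocaine, object, blur, rest, random) as the repeated factor".

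**Sample size.** Section C.2.e concludes for Aim 2 that "our proposed 60 completers participants per group should provide adequate statistical power". The 120 behind this comes from the Aim 1 calculation, "which will be rounded to 120 to provide balance with respect to gender".

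**The concern.** An independent-samples test takes the error variance of the drug contrast to be the sum of two unrelated variances. Here the same people supply both sets of maps, so whatever is stable in a person across the two days cancels from the drug difference. The planned test leaves it in the error term. The connectivity ANOVAs repeat the assumption, since scan condition is their only repeated factor.

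Three things are at stake:

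- **Drug effect (2b, 2d).** Standard errors are too large if the scans are positively correlated. A null result could then partly reflect the analysis, and the main statistical advantage of the crossover is lost.
- **Sex-by-drug effect (2c).** Section C.2.d lists a drug comparison and a sex comparison for regional activity, but not their interaction. The interaction is named only for the Aim 1 stress-task outcomes.
- **Women versus men.** If both scans per person enter this test as independent values, each person counts twice and the test gives too many false positives.

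The Aim 2 power statement does not say whether its groups are the two treatments or the two sexes, and it gives no within-person basis. That is a mismatched justification, not a shortage of participants.

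**Working it through.** **The plan's own figures.** From C.2.e: 140 × 3.35 / 4 = 117.25, taken as 118 and rounded to 120. At 80% retention, 120 / 0.80 = 150, against 152 recruited. Then 120 / 2 = 60 per group. The chain reproduces. Sixty per group fits 60 women and 60 men in a crossover, or 60 on each drug in a parallel design that this study does not use.

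**Inputs.** n = 120 completers with both scans (C.2.e). The contrast value from one scan has SD 1. r is the correlation between a person's two scans; the documents do not give it, so 0.1, 0.3, 0.5 and 0.7 are assumed. Tests are two-sided at 5%, one uncorrected comparison, using normal approximations. This illustrates the error term and is not the planned map-wise corrected test.

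**Formulas.**

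1. True SE of the drug difference is √(2(1−r)/n). The planned test uses √(2/n) = √(2/120) = 0.129. The ratio of planned to true is 1/√(1−r).
2. True size of the planned drug test: 2[1 − Φ(1.96/√(1−r))].
3. Power of the planned test at the effect where the paired test has 80%: Φ(2.80 − 1.96/√(1−r)).
4. Effect detectable with 80% power: paired 2.80·√(2(1−r)/120); planned 1.96·√(2/120) + 0.84·√(2(1−r)/120).
5. Size of the women v men test if both scans are pooled as independent: 2[1 − Φ(1.96/√(1+r))].
6. Difference in drug effect detectable for 2c, 60 women v 60 men on within-person differences: 2.80·√(2(1−r))·√(2/60).

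**Worked line at r = 0.5.** SE ratio 1/√0.5 = 1.41. Size 2[1 − Φ(1.96/0.707)] = 2[1 − Φ(2.77)] = 0.6%. Power Φ(2.80 − 2.77) = 51%.

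| Assumed r | 0.1 | 0.3 | 0.5 | 0.7 |
|---|---|---|---|---|
| Planned SE / true SE | 1.05 | 1.20 | 1.41 | 1.83 |
| True size of nominal 5% drug test | 3.9% | 1.9% | 0.6% | 0.03% |
| Planned power where paired has 80% | 77% | 68% | 51% | 22% |
| Detectable effect, paired (SD) | 0.34 | 0.30 | 0.26 | 0.20 |
| Detectable effect, planned (SD) | 0.36 | 0.34 | 0.33 | 0.31 |
| Women v men size, scans pooled | 6.2% | 8.6% | 11.0% | 13.3% |
| Detectable 2c difference (SD) | 0.69 | 0.61 | 0.51 | 0.40 |

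**Check by simulation (20,000 runs).** Size of the planned drug test: 0.040, 0.019, 0.005, 0.0005. Its power where the paired test has 80%: 0.77, 0.68, 0.51, 0.23. Pooled women v men size: 0.062, 0.086, 0.110, 0.132, against 0.049–0.050 with one averaged map per person. At an assumed per-comparison threshold of 0.001, the planned test has about 76%, 60%, 32% and 4% power where the paired test has 80%.

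**The case against.** **Hierarchy.** Section 5.1 names craving and stress response as the primary outcome, Specific Aim 2 is worded as exploring, and 2c and 2d are labelled exploratory. This stands, and it limits the weight of the point. Hypothesis 2b itself carries no exploratory label.

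**Harm at plausible effects.** C.2.e relies on 23 per group for 80% power. Read as a single two-sided 5% t-test, that implies an effect of about 0.84 SD for two groups, or 0.61 SD for one sample. Taking 0.61 SD on the single-scan scale, 0.61/0.129 − 1.96 is about 2.77, so even at r = 0 the planned test has over 99% power. The loss therefore matters for effects well below that benchmark, such as the 0.20–0.30 SD in the table. This too stands, but a valid test would detect those smaller effects from the same data.

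**Unknown correlation.** The analysed quantity is a cocaine-minus-neutral contrast, and subtraction may remove much of what is stable in a person. At r = 0.1 the loss is only from 80% to 77%. Nothing in the documents supports 0.7, and r may vary across the brain. The size of the loss is therefore uncertain, but the mismatch between design and test is not.

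**Women v men.** No text says the scans will be pooled, and no Aim 2 hypothesis is a sex main effect. The inflation is conditional and should be read that way.

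**Existing wording.** A random-effects analysis of subject-specific contrasts within a GLM might seem to cover the pairing. It does not: those contrasts are cocaine v neutral within one scan, and an independent-samples model has no participant term. The 2d ANOVAs could yield a gender-by-treatment term, but for connectivity only, and with treatment on the wrong level.

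**Conclusion.** The point holds. The Aim 2 design and its analysis contradict each other in two places, and nothing in the plan supplies a paired test or a participant term. The planned error term for drug is right only if a person's two scans are uncorrelated.

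Under positive correlation the consequence is lost power, not false drug findings. The loss is minor near r = 0.1 and substantial from about 0.3 upward, for effects near the paired test's detection limit. These sizes rest on assumed correlations, 120 people with both scans, and a single comparison before map-wise correction. Separately, 2c has no stated test for regional activity. Aim 1, where each person does the stress task once under one treatment, is untouched. This should be corrected before Aim 2 is analysed.

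**What to change.** **C.2.d, regional activity.** Test drug by a paired t-test on each person's oxytocin-minus-placebo contrast map, or by a mixed or flexible-factorial model with a subject factor. Include session (Day 2 or Day 3). When order is balanced this only adds precision, but dropout and the motion exclusion may unbalance order among those analysed. Test 2c by comparing women with men on the within-person difference maps. If a sex main effect is wanted, use one averaged map per person.

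**C.2.d, connectivity.** Make treatment a within-subject factor alongside condition, with gender between subjects.

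**Craving ratings in the scanner (2a).** C.2.d restates this hypothesis without naming a test. The same within-person model would serve.

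**C.2.e.** Define the groups. State Aim 2 as 120 completers each scanned under both treatments, with 60 women v 60 men for the sex-by-drug test.

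**Cost.** Plan wording and a different second-level design matrix; no new data. A participant with only one usable scan drops out of a simple paired test, but a mixed model can keep that scan. Making the change before analysis also avoids an unexplained switch of method afterwards.

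### Exploratory Hypothesis 2d: the connectivity analysis states no control for residual head motion beyond realignment and gross-motion exclusion, although the voxelwise model includes six movement parameters

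*Combined protocol and SAP*

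**What the plan says.** Section C.2.d (Statistical Methods) describes image processing for Aim 2 and then two analyses.

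- **Preprocessing.** "All volumes within a task run will be realigned to the first volume". After that, "scans with greater than one mm in three axes or one degree in three orientations will be excluded from group analyses". Normalisation follows, and then "the data will be smoothed with a 8x8x8 mm Gaussian kernel and will be high-pass filtered".
- **Voxelwise activation model.** "The GLM procedure is repeated for each voxel with six movement parameters", and these are "included as covariates to control for the influence of head motion on the data".
- **Connectivity (Exploratory Hypothesis 2d).** In each of 116 atlas regions, "the average intensity value at each time point will be extracted for each subject". Then: "The time series (shifted by one TR) will be segmented into four separate time series, one for each condition". Then: "Correlation matrices will then be computed for each subject and each condition and submitted to the BCT". The network and node metrics go into mixed ANOVAs with gender, treatment and condition as the only factors.

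The connectivity paragraph does not say which images the regional intensities come from. Hypothesis 2d covers resting-state as well as task connectivity, and section C.2.c.2 (Scanning Procedures) collects a separate 6-minute resting run. Realignment is described for task runs only.

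**The concern.** The plan treats motion left after realignment and exclusion as worth modelling in the activation analysis, but states no matching step where correlations are computed. Realignment corrects head position; it does not remove the signal changes that movement leaves in the time series. If such a change has the same sign in many regions, it raises their correlations together.

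A shift of that kind does not average out when a metric such as strength sums over links. If the amount of residual motion differs between oxytocin and placebo sessions, between men and women, or between picture conditions, the difference enters exactly the effects that the ANOVAs test. It could then be reported as oxytocin, sex or cue exposure reorganising brain networks.

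**Working it through.** The plan gives no sample size, power or motion figure for the connectivity analysis, so there is no stated number to reproduce. The check has two parts.

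**1. Steps side by side (section C.2.d)**

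| Step | Voxelwise model | Connectivity |
|---|---|---|
| Realignment | yes | not repeated; may be inherited |
| 1 mm / 1 degree exclusion | yes | may apply, since it is from group analyses generally |
| Smoothing, high-pass filter | yes | not stated; may be inherited |
| Six movement parameters | yes | none stated |
| Residuals, censoring or motion covariate | not needed for this comparison | none stated |

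Nor do the 20 random networks per subject remove motion: they preserve the weights and strength of the cocaine network, so any motion inflation passes into them.

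**2. Could residual motion matter? (illustration on assumed values)**

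From the documents: TR 2.5 s; six epochs; 24 s per block, one block per condition in each epoch; 60 completers per group; treatment analysed as between-subjects.

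- Volumes per condition: 6 × 24 / 2.5 = 57.6.
- Volumes in the cue run: four 24 s blocks make 96 s per epoch, so 6 × 96 / 2.5 = 230.4. The text also calls the epochs 90 s long, which gives 6 × 90 / 2.5 = 216.

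Assumed, because the documents give neither: a true correlation ρ = 0.30, and a share f of each region's variance that is common, same-sign residual motion. Then

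r_observed = ρ(1 − f) + f

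- f = 0.05: 0.30 × 0.95 + 0.05 = 0.335
- f = 0.10: 0.30 × 0.90 + 0.10 = 0.370
- f = 0.15: 0.30 × 0.85 + 0.15 = 0.405

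Shifts on the Fisher z scale with no true change in connectivity:

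- 0.05 v 0.10: atanh(0.370) − atanh(0.335) = 0.388 − 0.348 = 0.040
- 0.05 v 0.15: atanh(0.405) − atanh(0.335) = 0.430 − 0.348 = 0.081 (unrounded values)

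With an assumed between-person SD of 0.15 and 60 per group, the standard error of a difference is 0.15 × √(2/60) = 0.0274. The shifts are then 0.040 / 0.0274 = 1.5 and 0.081 / 0.0274 = 3.0 standard errors. A two-sided 5% test would declare them significant about 31% and 84% of the time.

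A simulation (58 volumes, 20 regions, ρ = 0.3, 60 per group, no true difference, 400 repetitions; outcome, the mean Fisher z over links) gave these rejection rates at the 5% level:

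| Motion shares | No regression | Six parameters regressed out |
|---|---|---|
| 0.05 v 0.05 | 5.5% | 3.3% |
| 0.05 v 0.10 | 98.8% | 6.0% |
| 0.05 v 0.15 | 100% | 3.0% |

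The 98.8% and 100% are upper bounds, because the simulation has no between-person variation. The recovery in the last column is also favourable: the simulated motion signal is an exact linear combination of the six parameters, which real motion need not be. Equal motion in both groups causes no excess of false positives. Only a difference does.

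**The case against.** The strongest reply has four parts.

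- **Motion is not ignored.** A reader might infer that raw images are correlated with no motion handling at all. The documents do not support that. Preprocessing is introduced for Aim 2 as a whole, Hypothesis 2d belongs to Aim 2, and the exclusion is from group analyses without restriction. This stands. What remains is that nothing beyond those steps is stated, whereas the activation model does go beyond them.
- **Silence is not omission.** The segmentation step cites published methods that might include nuisance regression. Their content cannot be used to fill the gap, and the paragraph otherwise lists its steps in order. An analyst following the text would regress nothing.
- **The size is invented and the mechanism unproven.** This largely stands. The motion shares are assumptions, and equal, same-sign motion in every region is close to a worst case. The volumes are treated as independent. The calculation concerns links and their mean rather than modularity, diversity or clustering. No document says that oxytocin, sex or cocaine pictures change head movement. Counterbalancing the order of sessions would not help, however, if the drug itself did.
- **The exclusion rule is only loosely worded.** A reader might take it to retain a scan with a large shift along one axis. A limit on each axis is an equally natural reading, so this calls for clarification and is not evidence that such scans would be kept.

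**Conclusion.** The point holds in limited form. As written, the connectivity analysis leaves residual motion in the correlations, while the plan's own activation model adjusts for it. Motion that differs by drug session, sex or condition could therefore appear as a connectivity effect.

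How large that effect would be cannot be derived from the documents. The 31% and 84% rest on ρ = 0.30, a between-person SD of 0.15 and motion shares of 5% against 10% or 15%, all assumed. They show that modest differences could matter, not that they will occur. A reader should not infer that the trial's connectivity results would be false, or that the main results are at risk. The reach is Exploratory Hypothesis 2d only: Aim 1, the sample size, cue-induced craving (2a) and the activation contrasts (2b, 2c) are untouched. The change is still worth making, because the parameters already exist and the method is better.

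**What to change.** 1. State that connectivity is computed from the preprocessed (realigned, filtered) images, and describe the same handling for the resting-state run.
2. Regress the six movement parameters out of each regional time series before segmentation and correlation.
3. Report mean displacement by drug session, sex and condition. Use it at most as a covariate in a sensitivity analysis: it is measured after dosing, so if the drug changes movement, adjusting for it could remove or bias part of a drug effect.
4. Clarify that the 1 mm / 1 degree exclusion applies to any axis or any orientation.

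**Cost:** analysis code only, with no new data and no change for participants. Regression uses about 6 of roughly 230 time-series degrees of freedom in the cue run (6 / 230 = 2.6%). If the exclusion rule would otherwise have been applied more leniently, a few more scans may be lost.
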